3.3.8. Scheduled DBS Tests

Participants in the DBS arm were instructed to collect DBS on the same day and at approximately the same time each week (Sunday through Wednesday to avoid delays due to weekend shipping). If a DBS sample PCR result is missing, it is considered as noncompliant to the scheduled DBS test, i.e. missed recommended DBS tests.

3.3.9. Confirmatory Whole Blood (WB) Tests

If positive CMV result was detected from a DBS test in participants in the DBS arm and recorded on the CMV Laboratory Data Upload eCRF, a confirmatory whole blood (WB) test will be performed by the study laboratory and recorded on the CMV Laboratory Data Upload eCRF. The confirmatory WB sample was collected within 3 days of the positive DBS sample.

3.3.10. Confirmatory DBS Tests

Participants that were required to undergo confirmatory WB testing were also required to produce an additional confirmatory DBS sample to provide additional virologic data to assess the performance of the DBS assay. Confirmatory DBS tests are DBS tests entered on the CMV Laboratory Data Upload eCRF with the same collection date as the WB samples recorded on the CMV Laboratory Data Upload eCRF. Note that Confirmatory DBS Tests will not be used to assess any outcome measures related to adherence to the weekly DBS collection schedule but will be used to assess Unanticipated Adverse Device Effects (Section 3.3.14).

3.3.11. Mobile Technology Reminder Failure

A Mobile Technology Reminder or Device Failure will be analyzed as one of the possible mechanisms for participants in the DBS arm to have non-compliance to the weekly DBS collection schedule. This failure will be defined as the occurrence of a failure to deliver the weekly DBS monitoring reminder message which may have prevented the scheduled monitoring test from being performed. The record of whether the weekly DBS monitoring reminder was sent is automatically generated by the Electronic Data Capture (EDC) system and stored in the Sent Notification eCRF.

For participants receiving both email and text message reminders, a failure is deemed to occur if either the email or text message was not sent. If the participant did not select a standard service provider, then only email notifications could be sent. The type of notification, i.e. whether it is the first or second reminder for an expected DBS test, is also saved. A second DBS reminder should be sent to a participant if a DBS test result record has not been uploaded within 4 days of their scheduled DBS test reminder. Because the second DBS

reminder could not be sent if the initial notification failed, descriptive analyses of device failures will be restricted to the status of the initial notification.

Failures will be identified by determining whether there are any days when a notification should have been sent, for which there is no record in the Sent Notification eCRF indicating that an initial reminder was sent. Participants in the DBS arm recorded their preferred day of the week for receiving the reminder on the DBS Testing Reminder eCRF. Participants were able to update the preferred day by submitting additional eCRFs. A failure is represented when there is no record in the Sent Notification eCRF where the recorded reminder date is the expected reminder date, and the reminder sequence number for the week is the first reminder.

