4.1 Randomized Cohort

Following consent, subjects in the DBS arm of the study will be asked to perform weekly DBS collection starting the week after discharge, once appropriate training has been provided (collection can be performed by a caregiver as long as appropriate training has been completed). Weekly reminders will be sent either as email or text messages. DBS samples will be mailed directly to the central lab (University of Washington) via pre-paid overnight mail (pick-up can be scheduled via the website or by phone through website) by the subjects. Results will be transmitted via a secure server to participating site staffs. The research staff will then contact the subjects' treating physicians via phone/fax notifying of positive results. The subjects will receive a notification via the study web portal when their positive CMV test results are available with a link to the secure website that can be used to access them. Text message reminders have been effective in randomized trials of medication adherence ^{5,38,39}, but too frequent reminders may be counterproductive. The web/mobile technology employed in this trial allows subjects to select method of electronic reminders (email and/or text message) and day and time of weekly electronic reminders. At minimum, one reminder will be sent before the recommended test.

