Number of positive confirmatory WB tests, n (%)	xxx (xx%)
Sensitivity	XX.X
Specificity	XX.X
Positive predictive value	XX.X
Negative predictive value	XX.X
Lin's Concordance Correlation Coefficient ^a between Confirmatory WB and Confirmatory DBS Testing	X.XXX
N= Number of participants in DBS arm with available samples for the Concordance analysis. Positive predictive value=Number of positive confirmatory whole blood tests / Number of positive	DBS tests.

^a Lin's Correlation between the Confirmatory WB and Confirmatory DBS Testing results (IU/mL).

Table 39: Mechanism of Non-Compliance - Mobile Technology DBS Testing Reminder Failures

Statistic	DBS (N=X)
Failed notifications, n	xxx
Participants with failed notification, n	XXX
Failed notification per participant for those with failed notifications, Median [Min, Max]	xxx [xxx, xxx]
Missed recommended tests, n	XXX
Participants with missed recommended tests, n	XXX
Missed recommended tests, with failed notifications within 7 days, n	XXX
Participants with missed recommended tests, with failed notification within 7 days, n	XXX
Number of Missed recommended tests per participant, Median [Min, Max]	xxx [xxx, xxx]
Number of missed recommended tests with failed notification within 7 days per participant, Median [Min, Max]	xxx [xxx, xxx]
N=Number of participants in the DBS arm in the ITT population.	1

Table 40: Mechanism of Non-Compliance to DBS Collection- Sample Failures

Statistic	DBS (N=X)
Missed recommended tests, n	xxx
Participants with missed recommended tests, n	xxx
Missed recommended tests, with failed sample collection, n	xxx
Participants with missed recommended tests, with failed sample collection, n	xxx
Missed recommended tests, with failed sample delivery, n	xxx
Participants with missed recommended tests, with failed sample delivery, n	xxx
Unevaluable samples, n	xxx
Participants with unevaluable samples, n	xxx
Note: N=Number of participants in the DBS arm in the ITT population. ^a An unevaluable sample is the equivalent of sample viability failure.	

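### SAP 3.3.11 gives two conflicting rules for a reminder failure in participants on both channels, and Table 39 does not tie a missed DBS test to its own week's reminder

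*SAP*

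**What the plan says.** SAP 3.3.11 starts from a concept: the failure of interest is "a failure to deliver the weekly DBS monitoring reminder message which may have prevented the scheduled monitoring test from being performed". It then gives two operational statements.

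- "For participants receiving both email and text message reminders", the SAP says, "a failure is deemed to occur if either the email or text message was not sent". The next sentence adds: "If the participant did not select a standard service provider, then only email notifications could be sent".
- The closing paragraph looks for days on which a notification was due and checks the log: "A failure is represented when there is no record in the Sent Notification eCRF where the recorded reminder date is the expected reminder date", limited to the first reminder of the week.

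Between the two, the section explains that because the second "reminder could not be sent if the initial notification failed, descriptive analyses of device failures will be restricted to the status of the initial notification".

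The results go to Table 39, whose title presents reminder failure as a mechanism of non-compliance. One of its rows is "Missed recommended tests, with failed notifications within 7 days, n". SAP section 13 describes the same summary as tests missed after a reminder had failed and gives no window. Under Protocol 4.1, subjects choose email, text or both, and at least one reminder precedes each recommended test.

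**The concern.** The two operational statements disagree on a week in which one of two requested messages went out. The participant was reminded, so the week does not fit the section's own idea of a failure that could have stopped the test. The either-channel sentence still counts it. Two programmers working from this text could produce different counts, and the SAP does not say which sentence governs.

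The link to missed tests is also loose. Reminders and DBS collections are both weekly, so a window as long as the cycle can tie a missed test to a reminder that belonged to another week.

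The number of mobile technology failures is a named exploratory outcome. Exploratory objective 2 asks for the mechanism of non-compliance, and Protocol 11.1.2 promises the relative contribution of reminders, subject adherence and kit failures. A count whose definition is unsettled, paired with tests by an unsettled rule, cannot answer that reliably.

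**Working it through.** The documents give no figure for this point, so there is none to reproduce. I set the rules side by side, then illustrate what the choice could mean under stated assumptions.

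**1. The two failure rules, for a participant on both channels**

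| Week | Either-channel rule | No-record rule, read literally |
|---|---|---|
| Both sent | not a failure | not a failure |
| One sent, one not | failure | not a failure |
| Neither sent | failure | failure |

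They differ only in the middle row. For participants on a single channel they agree.

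**2. How much the middle row could matter**

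Assume each channel fails with probability q and the two failures have correlation ρ. None of these inputs is in the documents. Then:

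- P(neither sent) = b = q² + ρq(1 − q)
- P(either not sent) = 2q − b
- share of flagged weeks in which one message was sent = (2q − 2b)/(2q − b)

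With q = 5%:

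| ρ | Either not sent | Neither sent | Share with one sent |
|---|---|---|---|
| 0 | 9.75% | 0.25% | 97.4% |
| 0.25 | 8.56% | 1.44% | 83.2% |
| 0.5 | 7.38% | 2.63% | 64.4% |
| 0.9 | 5.48% | 4.53% | 17.4% |
| 1 | 5.00% | 5.00% | 0% |

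The share depends little on q. For q from 1% to 10% it is 99.5% to 94.7% at ρ = 0, 66.2% to 62.1% at ρ = 0.5, and 18.0% to 16.5% at ρ = 0.9. Correlation drives it.

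**3. Dilution by single-channel participants**

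Let s be the share of participants on both channels, with q = 5% and ρ = 0. Flagged weeks are s × 9.75% + (1 − s) × 5%. Of these, s × 9.5% had one message sent.

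- s = 25%: 2.375/6.1875 = 38%
- s = 50%: 4.75/7.375 = 64%
- s = 75%: 7.125/8.5625 = 83%

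**4. The 7-day link**

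Put the failed reminder on day 0 and let its test fall due k days later (k is not given). The next week's test is then due on day k + 7 and the previous week's on day k − 7.

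- *Forward window:* the next test is reached only if k = 0 and day 7 counts as inside. For k of 1 or more it is due on day 8 or later, outside the window.
- *Undirected window, as Table 39 is worded:* the previous week's test lies 7 − k days before the failed reminder. For k from 1 to 6 that is 6 days down to 1 day, always inside. A test missed before the reminder failed could be paired with it.
- *Section 13's wording:* this excludes the previous week's test but sets no upper limit, so it does not confine the link to the same week either.

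**5. What the outputs show**

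Listing 10 has one yes/no field for whether a reminder was sent, even where the preference is both channels. Table 39 gives missed tests and failed notifications but not the number of scheduled DBS tests, so missed-test rates in reminded and unreminded weeks cannot be compared.

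**The case against.** The strongest reply is that the closing paragraph of 3.3.11 is the one that says how failures are found in the data. Read literally, it never flags a partly sent week. The reason given for dropping the second reminder also fits a complete failure best. On that reading Table 39 would be right about failures, and the either-channel sentence is a stray. This is a fair reading, but the SAP does not choose it. Someone could equally reconcile the text by applying the log check to each channel.

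The either-channel rule can also be defended as a count of technology failures: an unsent text is a fault even if the email went out. That stands for a technical tally. It does not stand for a table about why tests were missed, which is why both counts deserve a row.

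The analysis is descriptive. The SAP calls reminder failure one possible mechanism among several, and Table 39 shows total missed tests and total failed notifications separately. Questionnaires collect participants' own reasons. So the table links events and does not formally attribute them.

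Four stronger inferences are tempting and not supported:

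- **Table 39 overstates the technology share.** This depends on which rule is programmed, and no technology share is estimated.
- **A 39-fold overcount.** 9.75/0.25 = 39 needs q = 5% and independent channels. Both messages come from one data system, so shared failures are plausible.
- **A participant without a standard provider fails every week**, about 38 of them for a day-100 discharge. The either-channel rule covers people receiving both messages, and the next sentence reads naturally as an exception for those who can get only email. It needs stating, but the text does not impose this result.
- **The 7-day link doubles the attributed missed tests.** That would need the neighbouring test also to be missed and to fall in the window.

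**Conclusion.** The conflict in SAP 3.3.11 is real. For participants on both channels, a partly sent week is a failure under one sentence and not under another. If the either-channel rule is used, Table 39 can pair missed tests with weeks in which a reminder was sent, contrary to the section's own concept of a failure. Table 39 and section 13 also define the link differently, and neither confines it to the same week.

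The size cannot be stated. Under the assumptions above, the share of flagged dual-channel weeks with one message sent runs from nil, if the channels always fail together, to 95% or more, if they fail independently. Single-channel participants dilute it.

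The reach is limited to the exploratory mechanism summary in Table 39. The primary and secondary adherence endpoints use clinician-recommended tests taken from chart review (SAP 3.3.5 and 4.5.1) and do not depend on reminders.

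**What to change.** In SAP 3.3.11, section 13 and Table 39:

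1. For the non-compliance analysis, define a failure as no initial reminder sent by any channel on the expected date.
2. Show single-channel failures among dual-channel participants in a separate row, if sent status is stored by channel. The documents do not say whether it is.
3. State that participants without a standard service provider are treated as email-only.
4. Link each missed DBS test only to the reminder for its own week, and use the same wording in section 13 and Table 39 in place of the 7-day window.
5. Add the number of scheduled DBS tests, so that missed-test rates can be set side by side for reminded and unreminded weeks. Count them over the DBS compliance period in SAP 3.3.2, which already removes hospital days.

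The cost is wording in two sections and a few rows in one shell. Programming needs the laboratory upload data, which show the DBS results present and hence the tests missed, as well as the Sent Notification eCRF. No new data collection is needed, except that item 2 must be dropped if channel-level status was not kept.

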3.3.12. Sample Failures

DBS or WB sample collection failure will be identified when a participant in the DBS arm reports that the DBS or WB sample collection kit was not used due to a problem with the kit. DBS or WB kit problems were recorded by study staff in the Sample Collection Kit Problem eCRF. Frequencies of failures will be reported, and descriptions of the kit problems listed in detail.

Sample delivery failure is defined as any instance where a participant entered DBS or WB shipment data but there is no lab record entered for the expected DBS or WB test. Shipment data were entered by participants on the CMV Dried Blood Spot Shipment and CMV Whole Blood Shipment eCRFs.

Sample viability failure is defined as any instance where a participant entered DBS or WB shipment data and there is lab record entered for the expected DBS or WB test, but the DBS test result shows that the specimen is unevaluable. Results of the DBS or WB tests are entered into the CMV Laboratory Data Upload eCRF.

3.3.13. DBS Participant and Provider Satisfaction Measures

Participant questionnaires will be administered in the DBS arm after the third training visit, at one month post discharge, and at study completion. The provider questionnaire will be administered at study completion.

Questions on the questionnaires are measured on the Likert scale, on the binary scale (No or Yes), or measure the best response to each question. Regardless of measurement scale, all questions include a "Prefer not to answer" option. Questions asked on the Likert scale are for agreement (1-Strongly Disagree, 2-Disagree, 3-Neither Agree nor Disagree, 4-Agree, 5-Strongly Agree) or frequency (1-Never, 2- Very Rarely, 3-Rarely, 4-Occasionally. 5-Very Frequently). Answers to questions asked on the Likert scale will be converted to numbers ranging from 1-5 or missing if Prefer Not to Answer was selected. Answers to questions on the binary scale will be converted to 0 for No, 1 for Yes or missing for Prefer Not to Answer. Questions for which participants were to select the best response will be analyzed as categorical variables, where Prefer Not to Answer will be included as one of the levels of the variable.

For the questions asked on the Likert scale, a composite score will be calculated over all related questions at 1-month after discharge and end of study for participant satisfaction measures and at end of study for provider satisfaction measures (detail in Section 12.2).

3.3.14. Unanticipated Adverse Device Effects or Device Failures

False positive results and false negative results from the testing conducted at the University of Washington Laboratory on DBS samples are Unanticipated Adverse Device Effects (UADEs) and are considered Device Failures and will be reported as an Unanticipated Problem.

The following rules will be used to identify possible false positive or false negative results:

False Positive is reported in either of the following cases:

- A DBS sample is positive at a viral load above the treatment threshold at the respective site and a confirmatory WB sample is negative and collected within 3 days of the DBS sample.
- A confirmatory DBS is positive at a viral load above the treatment threshold at the respective site and a confirmatory WB sample is negative and collected on the same day.

False Negative is reported in either of the following cases:

- A CMV PCR result identified in the quarterly chart review is positive at a viral load above the treatment threshold at the respective site and a DBS sample is negative and collected within 3 days of the clinical plasma sample.
- A confirmatory DBS sample is negative and a confirmatory WB sample is positive at a viral load above the treatment threshold at the respective site collected on the same day.

Both DBS and WB results for UADE monitoring are obtained from the laboratory data uploaded by the University of Washington Laboratory (See Section 3.3.8 and Section 3.3.9 for further details).

4. INVESTIGATIONAL PLAN

4.1. Overall Study Design and Plan

This is a randomized clinical trial to assess whether self-collection of samples (DBS) that are mailed for testing to a central laboratory will improve the compliance with the clinical recommendation CMV testing of HCT recipients. 150 allogeneic HCT recipients \geq 15 years of age, who are considered by their transplant teams to be at risk for late CMV disease and who are clinically recommended to continue CMV monitoring after day 100 post-transplant, will be randomized (2:1) to participant self-collected DBS CMV monitoring with mobile technology support or standard of care with office-based testing. Randomization will occur when discharge from the transplant service is imminent, generally near day 100 post-transplant (enrollment window day 60-180 post-transplant). DBS self-collections will start the week after discharge. More than 85% of late CMV disease occurs within the first year after HCT [1]. While most patients are discharged to long-term primary care providers approximately 100 days after HCT, some may be discharged earlier, and some may stay longer with the transplant team due to complications. These latter patients are often at particularly high risk for late CMV complications and thus are important candidates for participation in this trial. For this reason, study entry is allowed up to 180 days (~6 months) after HCT and the duration of study participation is anticipated to be within a range of 26 weeks to 43 weeks. The transplant centers participating in this study have either a standard process where transplant recipients are offered to sign a consent to allow data from their charts to be accessed for retrospective trials or a waiver of additional consents for accessing charts for retrospective trials. This offers an opportunity to assess whether the study sample is representative of HCT population as a whole and to obtain a population-based estimate of later CMV disease. Therefore, clinical charts from an additional 450 HCT recipients (Observational Cohort) who meet eligibility criteria and have already consented for retrospective studies at the enrolling sites but are not participating in the DBS testing for CMV will be reviewed for the incidence and timing of CMV disease, morphologic relapse of the underlying disease, and death. Data from these participants will be used to assess whether the randomized study sample is representative of the DBS study population and to obtain a population-based estimate of late CMV disease participants.

The Schematic of the study design is also shown in Figure 1. The DSMB committee will be convened for an organizational meeting, ad hoc meetings to review safety data while the study is ongoing, and for a final meeting once the study has been completed after database lock. If the lower one-sided 90% confidence interval for the percent of participants experiencing CMV disease by one-year exceeds 8% (operationally 7 out of 50), a DSMB meeting will be convened. The DSMB will be charged with determining whether this exceptionally high rate of CMV disease has plausible clinical explanations related to the participant characteristics, or if it is the result of a failure in the monitoring system, and if so, what the source of the failure is (lack of compliance, failure of the system). Ultimately, they will make a recommendation to the PI as to whether any aspect of the study should be modified or terminated.

All enrolled participants will be followed for one year (365 days) post-HCT. Table 1 contains the schedule of events.

4.2. Discussion of Study Design, Including the Choice of Control Groups

The study is designed to compare adherence to clinician-recommended CMV-monitoring after discharge from HCT in participants simultaneously collecting DBS with mobile or web-based reminders compared with the current standard of care. An observational cohort of participants that were eligible for the randomized portion of the study, but were unable to participate in the randomized cohort, will also be followed to determine whether the participants in the randomized portion are representative of the general patient population meeting the inclusion criteria for the study.

